#### 1) Hospital re-admissions

##### a) Number of hospital admission

i) H0i: There is no difference in the cumulative number of hospital admissions for day i (null hypothesis); H1i: The cumulative number of hospital admissions for the standard discharge group is greater than that for the enhanced discharge group; for days  $i = 3, 7, 14, 21, 30, 60, 90$ .

ii) We will assess the groups for differences using Poisson regression model.

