**Rural Options at Discharge Model of Active Planning (ROADMAP):**

**Protocol and Statistical Analysis Plan**

## ***Methods***

### ***Settings***

This study was conducted in Montana, a state with a population of 989,417 people living on 145,546 square miles for an average density of 6.8 persons per square mile. St. Patrick Hospital (SPH) was the central site for this study. SPH, a member of the Providence Health and Services System, is a regional referral hospital (RRH) serving Western Montana and Eastern Idaho. SPH is located in Missoula, Montana, a city of 66,768 in a county of 109,299 people. SPH uses the Epic® electronic medical record system. This study focused on patients discharged from the RRH to one of four Montana counties served by critical access hospitals (CAH) that also used the Epic® electronic medical records system, including Beaverhead, Lake, Powell, and Sanders Counties.

The Montana Department of Public Health and Human Services designated all four of the counties involved in this study as rural counties (counties with less than 50 people per square mile). Furthermore, all four were non-metropolitan counties and three of the counties met the criteria of being a frontier county (population of less than 6 people per square mile). Travel time to Missoula from the principal town of the four counties ranged from 79 (76 miles) to 145 (172 miles) minutes. Portions of Lake and Sanders Counties are included in the Flathead Reservation, which is home to the Salish, Pend d'Oreille and Kootenai Tribes. Table 1 provides basic demographic data from the most recent U.S. Census for each of the four counties included in the present study.

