**Table 1**  
**Characteristics of Geographic Area**

County	Beaverhead	Powell	Lake	Sanders
Land Area (sq. miles)	5,541	2,326	1,490	2,760
Population	9,246	7,027	28,746	11,413
Density/Sq. Mile	1.7	3.0	19.3	4.1
White	94.9%	92.4%	68.2%	92.1%
Native American	1.8%	4.6%	23.4%	4.3%
Hispanic or Latino	3.7%	2.3%	4.0%	2.6%
Households	4,110	2,411	11,829	5,149
Mean Number in Household	2.11	2.31	2.38	2.17
Median Household Income	\$41,614	\$40,802	\$38,019	\$32,881
Per Capita Income	22,872	\$19,736	\$21,521	\$19,188
Percent Below Poverty	15.1%	15.3%	22.4%	22.0
Principal City Population	4,134	3,111	4,488	1,313

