### ***Patient Population***

All patients from these four selected counties admitted to SPH for treatment and at least one overnight stay during the period of October 19, 2015 through November 30, 2016 were eligible. Patients were included if they were being discharged home or to a swing-bed arrangement in their home county critical access hospital. Researchers excluded patients, if they were younger than 18 years old or older than 75 years old, were prisoners of the State correctional facility in Powell County, came from or were being discharged to a nursing home or other long-term care facility, were admitted with a primary diagnosis of a psychiatric impairment or substance abuse, were actively dying, or presented cognitive impairments that would significantly limit their ability to consent or to complete the measurement instruments (Flesch-Kincaid Reading Level = 7.5). Figure 1 presents a patient flow diagram.

[figure not shown]

Figure 1: Patient flow diagram of the ROADMAP study.

**Enrollment.** A Research Transitions Coordinator (RTC) received a daily report of patients admitted into SPH. She reviewed the report to identify eligible patients. Based on the review, she developed a list of eligible patients. She then reviewed the list to identify patients who met any of the exclusion criteria; this produced a list of patients who met inclusion criteria to recruit into the study. Next, the RTC went to each patient's room to explain the study, to identify any additional factors that might exclude the patient, and to determine a patient's willingness to participate. If a patient met inclusion criteria and expressed interest, the RTC reviewed the informed consent material and enrolled the patient.

The RTCs screened 751 patients from the four counties. Of those, 570 patients were excluded as ineligible based on exclusion criteria, 54 who met the inclusion criteria declined to participate in the study, and 127 enrolled in the study. Table 2 presents demographic information of participants by experimental condition as required by ClinicalTrials.gov.

Table 2

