### ***Design***

We used a quasi-experimental time series design with switching replications (Cook & Campbell, 1984). This design involved starting enrolled patients from each of the four counties in a baseline condition. Then, once a stable rate of enrollment had been reached, the introduction of the experimental procedures was staggered across patients from each county over time. That is, all patients from one county were enrolled into the intervention while those from the other counties remained in baseline. Later, patients from a second and third county were added to the intervention condition while those from the remaining county remained in baseline; and so on. Finally, a return to baseline condition was initiated for patients from all

four counties. This design protects against most threats to the internal validity of findings and many threats to their external validity. It is particularly helpful in protecting against threats posed by seasonal variables. A final "return to baseline" phase was also included in the study to add to protections from threats posed by interactions.

**Baseline and experimental conditions.** Patients in baseline conditions received the standard discharge services. Patients enrolled in the experimental condition received the standard discharge services and the Enhanced Discharge Planning and Rural Transition Supports.

**Measures.** All patients completed the PAM10 (Hibbard & Mahoney, 2005) and provided selected demographic information at the time of enrollment. Other demographic information was collected from each enrolled patient's medical record. In addition, we collected the LACE+ rating from the medical record and the rating of needs from our Rural Transition Needs Assessment. The LACE+ is a compilation of medical and treatment factors (e.g., chronic conditions, previous hospitalizations) derived from a patient's medical record that are used to assess risk for re-hospitalization (van Walraven, Wong, & Forster, 2012).

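### Condition was set by county and calendar period, but no SAP model names a county or calendar term, so the primary contrasts are open to county confounding and the claimed seasonal protection goes unused

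*Combined protocol and SAP*

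**What the plan says.** The Design section describes a quasi-experimental time series with switching replications. Every county began in baseline. The first switch is described thus: "all patients from one county were enrolled into the intervention while those from the other counties remained in baseline". The next step took in two more counties at once, leaving a single county unswitched: "patients from a second and third county were added to the intervention condition while those from the remaining county remained in baseline". The study ended with a joint move of the four counties back to standard care (the text reads "a return to baseline condition was initiated for patients from all" of them). On what this arrangement achieves, the section says: "It is particularly helpful in protecting against threats posed by seasonal variables". Accrual is set under Patient Population: admissions "during the period of October 19, 2015 through November 30, 2016 were eligible". The text gives no switch date for any county and no date for the return to baseline.

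The SAP calls the hypotheses on hospitalisations and emergency department visits primary. For counts of admissions the whole specification is "We will assess the groups for differences using Poisson regression model". Emergency department and PCP visit counts have the same wording, and the proportions are given logistic regression in equally brief terms. SF-12 and RTM14 are to be modelled on treatment group by repeated measures ANOVA. The time periods there are follow-up occasions, not calendar time. Nowhere in hypotheses 1 to 7 is county, switch step, phase, season or calendar date named as a term, and no within-county or time-series analysis is described.

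**The concern.** When a patient's condition depends on where and when the patient was admitted, the two groups can differ in county and in season before the intervention does anything. The protection in a staggered design comes from comparisons within county, and between counties that are in different conditions on the same dates. A model holding only a two-level group variable uses neither. It compares all enhanced patients with all standard patients, whatever their county or date.

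If event rates differ by county or over time, the primary rate ratios and odds ratios mix that difference with the effect of the intervention. This could create an apparent benefit or hide a real one. With nothing prespecified, the decision to adjust is also left until outcomes can be seen.

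**Working it through.** The documents state no event rate, alpha, power or sample size calculation, so there is no figure of the plan's own to reproduce.

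**Inputs (Table 4; Baseline A / Intervention / Baseline B).** Sanders 10 / 21 / 4; Beaverhead 8 / 8 / 0; Powell 11 / 6 / 2; Lake 34 / 15 / 8; totals 63 / 50 / 14 = 127. The SAP does not define standard; I take it as Baseline A plus B.

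**1. County mix.**

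| County | Standard (n=77) | Enhanced (n=50) |
|---|---|---|
| Sanders | 14 (18.2%) | 21 (42.0%) |
| Beaverhead | 8 (10.4%) | 8 (16.0%) |
| Powell | 13 (16.9%) | 6 (12.0%) |
| Lake | 42 (54.5%) | 15 (30.0%) |

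Pearson chi-square is 11.55 on 3 df, p=0.009. With Baseline A alone as standard it is 11.40, p=0.010, so the imbalance does not depend on how Baseline B is handled.

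**2. What the mix alone can do to the crude rate ratio.** With no treatment effect, the two-group Poisson model estimates

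RR = (Σ enhanced count × county rate / 50) ÷ (Σ standard count × county rate / 77).

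Set one county's rate to k times the others' (assumed). For k = 2:

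- Lake: ((50 + 15)/50) ÷ ((77 + 42)/77) = 1.300/1.545 = 0.84
- Sanders: ((50 + 21)/50) ÷ ((77 + 14)/77) = 1.420/1.182 = 1.20

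| County with the higher rate | k = 1.5 | k = 2 | k = 3 |
|---|---|---|---|
| Lake | 0.90 | 0.84 | 0.77 |
| Sanders | 1.11 | 1.20 | 1.35 |
| Powell | 0.98 | 0.96 | 0.93 |
| Beaverhead | 1.03 | 1.05 | 1.09 |

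**3. Effect on the test.** Simulation on the Table 4 allocation. Assumed: 0.15 events per patient, doubled in one county; one-sided 5% Wald test, because the alternatives for admissions and ED visits are one-sided.

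| Scenario | Crude model | With county |
|---|---|---|
| No effect, Lake doubled: rejects | 9.9% | 4.4% |
| No effect, Sanders doubled: rejects | 1.7% | 4.9% |
| True RR 0.5, Sanders doubled: median RR, power | 0.59, about 22% | 0.50, about 34% |
| True RR 0.5, equal county rates: power | about 27% | about 24% |

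**4. Precision cost of county.** Variance factor = (77 × 50/127) ÷ Σ(standard × enhanced/total by county) = 30.31 ÷ (8.40 + 4.00 + 4.11 + 11.05) = 30.31/27.56 = 1.10. The square root is 1.05, so the standard error rises by about 5%. With Baseline A alone the factor is 27.88/25.06 = 1.11.

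**5. Season.** October 19, 2015 to November 30, 2016 is 409 days inclusive. One full cycle is 366 days (2016 was a leap year), so 409 − 366 = 43 calendar dates occur twice. Season can therefore be separated from condition mainly through counties that were in different conditions on the same dates. The return to baseline adds little: it applied to all counties, has 14 patients and has none from Beaverhead. Without switch dates, neither the seasonal bias nor the precision cost of a calendar term can be calculated.

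**The case against.** **The SAP does not forbid covariates.** True. The finding is that none is prespecified.

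**Staggered switching makes county imbalance expected.** Also true. A reader might infer from p=0.009 that the contrast is confounded or that assignment went wrong. The p-value shows neither: it describes the mix, and the mix biases nothing unless event rates differ by county.

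**Table 1 might be taken to show that the conditions differ in risk.** It does not. Weighting the "Percent Below Poverty" row by Table 4 gives (14×22.0 + 8×15.1 + 13×15.3 + 42×22.4)/77 = 20.4% for standard and (21×22.0 + 8×15.1 + 6×15.3 + 15×22.4)/50 = 20.2% for enhanced. The county percentages of Native American residents would predict 14.5% and 9.7%. The enrolled patients in Table 2 run the other way: 7/77 (9%) and 6/50 (12%). On distance the text says only "Travel time to Missoula from the principal town of the four counties ranged from 79 (76 miles) to 145 (172 miles) minutes", a range that cannot be tied to the imbalance. The assumed county rate ratios therefore have no support in the documents. They show sensitivity, not expected bias.

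**The gain in overall accuracy is modest.** Simulated mean squared error of the log rate ratio under no effect, crude against county-adjusted, is 0.28 and 0.30 with equal rates, 0.23 and 0.20 with Lake doubled, and 0.224 and 0.216 with Sanders doubled. This stands. The case for county rests on removing bias and holding test size, not on a smaller total error.

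**County indicators might seem unworkable at the sparse early days.** A county with no events loses only its own coefficient and drops out of the Poisson treatment contrast. That is no reason to omit the term.

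**County adjustment does not deal with season.** This stands, and it is why a separate calendar analysis is needed.

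**Conclusion.** The concern holds and should be corrected before the primary analysis. Assignment by county and period, the absence of any county or calendar term, and the county imbalance all come directly from the document. Followed as written, the primary contrasts are open to county confounding that a four-level term would remove.

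Size and direction are unknown because no county event rates are given. The null rate ratios of 0.84 and 1.20 depend on the assumption that one county's rate is double the others'; with equal county rates there is no such bias. The simulated rejection rates depend further on the assumed 0.15 events per patient and one-sided 5% level.

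On season the conclusion is narrower. The protection claimed in the Design section is not carried into any model. A reader might infer a seasonal bias of some particular size, but any such figure would reflect invented switch dates, and the documents support none.

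**What to change.** 1. Put county as a four-level fixed effect in the main model for each of hypotheses 1 to 7. With only four counties, a random county effect or cluster-robust errors would be unreliable.
2. State each county's switch date, the date of return to baseline, and whether standard means Baseline A plus B.
3. Beside each county-adjusted estimate, report an analysis that also adds calendar period of discharge, in a few date-based categories chosen without reference to outcomes. Name this as the analysis that addresses season, and limit the seasonal-protection claim to what it supports.
4. Disclose that enrolment was complete and the county counts known when these terms were chosen, so they are not fully prespecified.

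**Cost.** SAP text and the dates. County is already tabulated, and discharge dates must exist because the evaluation packages are timed from discharge. County raises the variance by a factor of about 1.10 (standard error about 5% larger). If county rates are in fact equal, simulated power at an assumed rate ratio of 0.5 falls by about 2 to 3 points. The calendar term costs more, by an amount that depends on the unstated switch dates, which is why it is reported beside the main estimate and not in place of it.

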## Demographic Characteristics of Study Sample Required for Clinical Trials

	Baseline A	Intervention	Baseline B	Totals
Enrolled	63	50	14	127
Completed	62	47	13	122
Lost to Follow-up	1	3	1	5
Under 18 Years of Age	0	0	0	0
Between 18 and 65	37	26	10	73
Over 65	26	24	4	54
Female	28	21	6	55
Male	35	29	8	72
American Indian, Alaskan	5	6	2	13
Asian	0	0	0	0
Hawaiian or Islander	1	0	0	1
Black or African American	0	0	0	0
White	56	43	11	110
More than one race	0	0	0	0
Unknown or Not Reported	1	1	1	3
Subtotal	63	50	14	127
Hispanic or Latino	0	0	0	0
Not Hispanic or Latino	61	47	11	119
Unknown or Not Reported	2	3	3	8
Subtotal	63	50	14	127

In addition, Table 3 presents the number of patients excluded by criterion and Table 4 shows the number of patient enrolled in the study from each county by experimental condition.

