Researchers prepared an evaluation package that included the three-item Care Transition Measure (Coleman, Mahoney, & Parry, 2005), the 12 item Short Form of the Medical Outcome Study (Stewart and Ware, 1992), and a Rural Transitions Measure (RTM14; Montana Team, 2016). The RTM14 asked patients to report whether they strongly agree, agree, disagree, or strongly disagree with each of 14 statements reflecting services provided after discharge to facilitate an effective transition home. Researchers also asked patients to report the number of times that they had seen a PCP, visited an emergency department of any hospital, been admitted to SPH, or been admitted to any other hospital since they were discharged or since their last report.

**Data collection.** We asked patients to complete the instruments in the evaluation package at 3, 7, 14, 21, 30, 60, and 90 days after they were discharged from the RRH. RTCs gave patients the 3 and 7 day evaluation packages in the RRH to complete at home. The research staff mailed the remainder of the evaluation packages to patients three days before the end of each measurement period. Each evaluation package included an instrument and a

self-addressed stamped envelope for returning a completed questionnaire. In addition, the first six instruments included a \$10 honoraria and the last packet included a \$40 honoraria.

Finally, we used information in the Epic® patient records to collect demographic data and information on emergency department visits, outpatient admissions, and hospitalizations at the participating hospitals. Finally, RTCs and LCTC kept notes detailing the patient situation and experiences that were posted in the EOC tab in Epic®.

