### ***Statistical Analysis Plan***

The primary hypotheses address the question of whether the intervention makes a difference in the frequency of hospitalizations and emergency department visits. There are at least two ways to view the measurement of these outcomes. The first is to examine the total number of hospital or emergency department visits in each condition. The second is to examine the proportion of patients who have at least one hospital or emergency department visits in each condition.

In addition, there are several intermediary outcomes we anticipate. These relate to the physical and mental health of patients, the rating of the quality of discharge planning services, and the rating of the delivery of rural transition services. We will test the following hypotheses using specified procedures:

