##### b) Proportion of patients with at least one hospital admission

i) H0i: There is no difference in the proportion of patients who report a hospital readmission for day i (null hypothesis); H1i: The proportion of patients who report a hospital readmission for the standard discharge group is greater than that for the enhanced discharge group; for days  $i = 3, 7, 14, 21, 30, 60, 90$ .

- ii) We will assess the groups for differences using logistic regression.
- 2) Emergency department visits
- a) Number of emergency department visits
    - i) H0i: There is no difference in the cumulative number of ED visits for day i (null hypothesis); H1i: The cumulative number of ED visits for the standard discharge group is greater than that for the enhanced discharge group; for days  $i = 3, 7, 14, 21, 30, 60, 90$ .
    - ii) We will assess the groups for differences using Poisson regression model.
  - b) Proportion of emergency department visits
    - i) H1i: The proportion of patients who report at least one ED visits for the standard discharge group is greater than that for the enhanced discharge group; for days  $i = 3, 7, 14, 21, 30, 60, 90$ .
    - ii) We will assess the groups for differences using logistic regression model.
- 3) Primary care provider (PCP) visits
- a) Number of PCP visits
    - i) H0i: There is no difference in the cumulative number of PCP visits for day i (null hypothesis); H1i: The cumulative number of PCP visits for the standard discharge group is greater than that for the enhanced discharge group; for days  $i = 3, 7, 14, 21, 30, 60, 90$ .
    - ii) We will assess the groups for differences using Poisson regression model.
  - b) Proportion of PCP visits
    - i) H0i: There is no difference in the proportion of patients who report at least one PCP visits for day i (null hypothesis); H1i: The proportion of patients who report at least one PCP visits for the standard discharge group is greater than that for the enhanced discharge group; for days  $i = 3, 7, 14, 21, 30, 60, 90$ .
    - ii) We will assess the groups for differences using logistic regression model.
- 4) Physical health as measured by the Short Form (SF12) functional health score

- a) Hoi: There is no difference in mean SF-12 Physical Health scores between the standard and enhanced discharge groups (null hypothesis); H1i: The mean SF-12 Physical Health scores differ between the standard and enhanced discharge groups.

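### Repeatable events (primary hypotheses 1a and 2a) are tested by Poisson regression with no provision for overdispersion, so standard errors are likely too small where cumulative counts are not low

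*Combined protocol and SAP*

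**What the plan says.** The Statistical Analysis Plan section frames the primary question as "whether the intervention makes a difference in the frequency of hospitalizations and emergency department visits" and offers two ways to look at it. On the count view it says: "The first is to examine the total number of hospital or emergency department visits in each condition". The other view is the proportion of patients with at least one event.

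The count hypotheses are 1(a) for hospital admissions and 2(a) for ED visits, both primary, and 3(a) for PCP visits, which is not named as primary. Each is tested on cumulative counts at days 3, 7, 14, 21, 30, 60 and 90. The alternatives point one way; for ED visits the alternative reads "The cumulative number of ED visits for the standard discharge group is greater than that for the enhanced discharge group". The stated method is the same for all three: "We will assess the groups for differences using Poisson regression model".

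Two statements in the Measures paragraphs of the Design section bear on this:

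- Repeat events count. Researchers "asked patients to report the number of times that they had seen a PCP, visited an emergency department of any hospital", and likewise the number of admissions.
- LACE+ is taken from the medical record and is "used to assess risk for re-hospitalization". It enters none of the models in the plan.

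The documents mention no dispersion check, scale parameter, robust variance, negative binomial alternative or covariate for these models. They state no significance level, event rate or power.

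**The concern.** If patients have different underlying rates, the variance of their counts exceeds the mean, and a Poisson model that assumes equality reports standard errors that are too small. Collecting a readmission risk score presumes such differences for admissions. Eligibility is also broad: adults up to 75 with an overnight stay, not limited to one index condition. For a given spread of risk, variance/mean rises with the mean, so cumulative counts are most exposed at the later days.

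At stake are 2 outcomes × 7 days = 14 tests on the count side of the primary question. Where counts are overdispersed, p-values and intervals would overstate the evidence, and a few frequent users could carry undue weight.

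A smaller point concerns wording. The hypotheses compare group totals, but the groups differ in size: 63 + 14 = 77 standard (both baselines pooled) against 50 enhanced. With identical rates the standard total would be expected to be 77/50 = 1.54 times the enhanced total. A Poisson fit with one record per patient over a common window already compares means per patient, so only the wording needs correcting.

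**Working it through.** The plan has no sample size or dispersion figure to reproduce, so the check asks how far the test departs from its nominal level under stated assumptions.

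**Inputs from the documents.** Group sizes 77 and 50 (Table 2, baselines pooled); completers 62 + 13 = 75 and 47; direction standard > enhanced.

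**Assumptions.** Nominal level 5%; mean count per patient m from 0.05 to 1.0, the same in both groups; gamma-Poisson counts with dispersion k = 1 to 2, and k = 0 for no overdispersion.

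**Formulas.**

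- variance/mean = 1 + k·m
- shortfall of the Poisson standard error = 1 − 1/√(1 + k·m)
- approximate true one-sided error = 1 − Φ(1.645/√(1 + k·m))

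At m = 0.5, variance/mean is 1.5 (k = 1) or 2.0 (k = 2):

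- shortfall: 1 − 1/√1.5 = 18%; 1 − 1/√2.0 = 29%
- approximate one-sided error: 9.0% and 12.2%

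**Simulation.** 77 v 50 patients, no group effect, 40,000 replicates per setting. The test is a Wald test of the log ratio of means per patient, with Poisson variance 1/total₁ + 1/total₂. Data sets with an empty group count as non-rejections. Ranges are for k = 1 to 2.

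| Mean per patient | Variance/mean | SE too small by | True error, one-sided | True error, two-sided |
|---|---|---|---|---|
| 0.05 | 1.05–1.1 | 2–5% | about 1% or less | about 1% or less |
| 0.1 | 1.1–1.2 | 5–9% | 3.4–4.2% | 3.5–4.1% |
| 0.2 | 1.2–1.4 | 9–15% | 5.6–7.3% | 6.2–8.5% |
| 0.5 | 1.5–2.0 | 18–29% | 8.2–11.9% | 10.5–16.2% |
| 1.0 | 2.0–3.0 | 29–42% | 12.1–16.5% | 16.1–25.1% |

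Repeat runs agree to within about one percentage point. With the completers (75 v 47) the one-sided error is 8.3–11.5% at mean 0.5 and 11.8–16.6% at mean 1.0.

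**Controls.** With k = 0 at mean 0.5, Poisson holds its level (4.7–4.8%). At mean 0.05 sparse data make the test conservative, and in about 11% of data sets one group has no events.

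**Alternatives on the same kind of data, mean 0.5.**

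- Sandwich standard errors: 5.3–5.9%.
- Negative binomial by maximum likelihood (3,000 replicates): 5.3–5.8%.
- Poisson with a Pearson scale factor (completers, one-sided): 4.4–4.8%.

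At mean 1.0 sandwich errors reach at most 6.2%.

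**Offset for time observed.** Table 2 lists five patients under "Lost to Follow-up": 1 + 1 = 2 standard and 3 enhanced. If each was lost mid-window, the ratio moves by ((77 − 2 × 0.5)/77) / ((50 − 3 × 0.5)/50) = 1.018. If all five contribute no time it is (75/77)/(47/50) = 1.036. The extremes are 75/77 = 0.97 and 50/47 = 1.06. This is a minor matter.

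**The case against.** The strongest reply is that the inflation is assumed. The documents give no event rate, repeat-event frequency or dispersion; with none, Poisson is adequate, and at means of 0.1 or below it does not exceed 5% even with k = 2. Material inflation needs roughly 0.5 events per patient or more, and nothing shows which of the seven days would reach that. This stands as a limit: the 14 tests are those the method covers, not those shown to be affected.

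LACE+ bears on readmission only and gives no figure for the spread of risk here, so it supports the argument for 1a more directly than for 2a or 3a. That also stands.

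The alternatives are directional, so the one-sided figures should lead; the plan does not state the sidedness of its tests, so both are shown.

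Hypotheses 1b and 2b use logistic regression on having at least one event and are not driven by repeat use. That limits the harm, but they answer a different question.

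Finally, naming Poisson regression does not rule out a robust variance. True, but the plan does not say one will be used, and leaving that choice until the data are seen is discretion a plan should remove.

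**Conclusion.** The concern holds. The omission is a fact of the text. Its consequence is likely, not certain, and is confined to days on which cumulative counts are not low. Under the assumed dispersion (k = 1 to 2) and a 5% one-sided test, the true error rate is 5.6–7.3% at 0.2 events per patient, 8.2–11.9% at 0.5 and 12.1–16.5% at 1.0. There is no inflation at 0.1 or below, or without overdispersion. The actual size in this trial cannot be fixed from the documents. The calculation also treats patients as independent. This should be corrected: it affects half of the primary analyses, the companion proportion tests soften the effect on conclusions, and the remedy is cheap.

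**What to change.** In items 1(a), 2(a) and 3(a) of the Statistical Analysis Plan:

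- State each hypothesis as a ratio of events per patient, standard v enhanced.
- Fit one record per patient at each analysis day, using either Poisson regression with robust (sandwich) standard errors or a negative binomial model, and name which one in advance.
- Include log(days observed up to that day) as an offset. This is a refinement worth about 2%. It needs each patient's days under observation; Table 2 gives only the number lost.
- Say what will be reported when a group has no events at an early day.

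The cost is a few lines of text and one option in the model call, with no new outcome data. If the counts are overdispersed, intervals widen (median standard error about 19–36% larger in the mean 0.5 scenarios); if they are not, intervals are almost unchanged.
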